8.1 Definition of Adverse Event

An adverse event (AE) is defined as any untoward medical occurrence associated with the use of an intervention in humans, whether or not considered intervention related.

8.2 Definition of Serious Adverse Event

An AE that results in any of the following outcomes is defined as a Serious Adverse Event:

- Death,

- Life-threatening adverse experience*,
- Inpatient hospitalization or prolongation of existing hospitalization,
- Persistent or significant disability/incapacity,
- Congenital anomaly/birth defect, or cancer, or
- Any other experience that suggests a significant hazard, contraindication, side effect or precaution that may require medical or surgical intervention to prevent one of the outcomes listed above,
- Event that changes the risk/benefit ratio of the study.

*A life-threatening adverse experience is any AE that places the patient or subject, in the view of the investigator, at immediate risk of death from the reaction as it occurred, i.e., it does not include a reaction that, had it occurred in a more severe form, might have caused death.

8.3 Classification of Adverse Events

8.3.1 Severity

Adverse events are graded according to the Common Terminology Criteria for Adverse Events (CTCAE) as developed and revised by the Common Therapy Evaluation Program (CTEP) of the National Cancer Institute.

8.3.2 Attribution

Adverse events are further given an assignment of attribution or relationship to study intervention or procedure. Attribution categories are:

- **Definite** – The adverse event is clearly related to the study intervention or procedure.
- **Probable** – The adverse event is likely related to the study intervention or procedure.
- **Possible** – The adverse event may be related to the study intervention or procedure.
- **Unrelated** – the adverse event is clearly not related to the study intervention or procedure.

8.3.3 Expectedness

An adverse event is considered unexpected if it is not listed in the investigator brochure or package insert(s), or is not listed at the specificity or severity that has been observed, or, if an investigator brochure is not required or available, the event is not consistent with the risk information described in the general investigational plan or elsewhere in the current application.

8.4 Adverse Events Monitoring

This study is a minimal risk level study that does not require monitoring by the HDFCCC Data and Safety Monitoring Committee (DSMC) as per the National Cancer Institute-approved Data and Safety Monitoring Plan. Ultimately, the PI is responsible for the safety and conduct of this study.

8.5 Follow up of Adverse Events

All participants who experience adverse events will be followed with appropriate medical management until resolved or stabilized, as determined by the investigator.

8.6 Documenting and Reporting of Adverse Events

Adverse Events will be documented in the study Case Report Forms (CRFs) and reported to the IRB, HDFCCC DSMC, and collaborators in accordance with all applicable institutional and regulatory requirements.

9 Statistical Considerations

9.1 Sample Size Considerations

9.1.1 Sample Size and Power Estimate

Our study is powered to assess both the primary outcome of smoke-free home adoption ≥ 90 days and the secondary outcome of point prevalence abstinence at 6-months follow-up. We designed the RCT to detect medium-large effect sizes, which are consistent with estimates from our pilot study¹⁴ and from other studies of brief interventions to increase adoption of smoke-free homes (intervention effect $\geq 40\%$ versus control effect $\sim 25\%$).^{32,139} Power analyses assumed 80% power; two-tailed alpha of 0.05; N=400 smoking residents recruited from 20 PSH units; 80% retention at 6-months; average 6-month site cluster size of 16 residents; group comparisons of 6-month binary outcomes describing adoption of a smoke-free home for ≥ 90 days and point prevalence abstinence from preliminary data, expected 6-month control group outcome rates of 12% and 4% for smoke-free home adoption and point prevalence abstinence, respectively; from preliminary data, intra-site outcome correlations of 0.077 (ρ_{SFH}) and zero (ρ_{PPA}); and mixed logistic models including random intercepts for sites. Estimated design effects equaled $1+(16-1)\rho_{SFH}=2.16$ and $1+(16-1)\rho_{PPA}=1.0$, respectively. For the primary outcome of voluntary smoke-free home adoption, the minimum detectable effect for the intervention group is 30.3% compared to 12% for the control group, which compares favorably with 31.3% obtained in our pilot study as well.¹⁴ For the secondary outcome of point prevalence abstinence at 6 months, the minimum detectable effect in the intervention group is 12.6% compared to 4% in the control group, which compares favorably with 16.9% obtained in the pilot study.¹⁴

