1.2 Background on study intervention

There are several approaches to implementing smoke-free policies in housing such as having a city ordinance restricting smoking in multi-unit housing or housing providers mandating smoke-free policies on their properties. However, these approaches may be difficult to implement in PSH for several reasons. First, there is concern that mandated policies conflict with PSH's harm reduction framework,⁹ potentially increasing risk of unsheltered homelessness if people left PSH because of the policy or were evicted because of a policy violation. Second, PSH staff may lack resources and time to enforce a smoke-free policy even if they put one into effect.⁹ However, in the absence of smoke-free policies, PSH residents are unprotected from secondhand smoke exposure unless they voluntarily adopted smoke-free homes. Thus, research is needed to: (a) determine whether individually-directed strategies are effective in

increasing voluntary adoption of smoke-free homes among PSH residents, and (b) determine whether these strategies can be brought to scale within PSH.

In our previous pilot study, we conducted a single-arm trial of an intervention to increase voluntary adoption of smoke-free homes, i.e., a voluntary no-smoking rule in one's home, among 100 formerly homeless adults in PSH.¹⁴ The multi-faceted voluntary smoke-free home intervention acted upon the individual, social and organizational levels to modify tobacco use behavior. The intervention consisted of providing a step-by-step guide to residents on how to voluntarily adopt a smoke-free home as well as training PSH staff on how to refer residents to local cessation resources. At 6 months, 31% of residents adopted a voluntary smoke-free home compared to 12% at baseline.

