4.1 Eligibility Criteria

4.1.1 Inclusion Criteria

In order to be eligible to participate in this study, an individual must meet all of the following criteria:

1. Age 18 years or older
2. Ability to understand study procedures and to comply with them for the entire length of the study.
3. Ability of individual or legal guardian/representative to understand a written informed consent document, and the willingness to sign it.
4. Current smokers [(smoked at least 100 cigarettes in lifetime, daily or non-daily smoking in the past 7 days and at least 5 cigarettes per day, verified by expired Carbon Monoxide (CO) \geq 8 parts per million (ppm)]⁷⁷ who smoke in their homes.
5. Expect to live in the PSH site for at least 12 months, and
6. English proficient.

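### Section 9.1.1 overstates the design's power: the 30.3% v 12% figure reproduces, but power is about 50% at the low end of the cited contrast, the margin over the pilot vanishes on 18 df, and the 12% control rate is doubtful

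*Combined protocol and SAP*

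**What the plan says.** Section 9.1.1 sets out the calculation: "Power analyses assumed 80% power", "two-tailed alpha of 0.05", "N=400 smoking residents recruited from 20 PSH units", 80% retention, 16 residents per site at 6 months, and an intra-site correlation of 0.077 for smoke-free home adoption and zero for abstinence. The control rates are "expected 6-month control group outcome rates of 12% and 4% for smoke-free home adoption and point prevalence abstinence"; as the sentence reads, they come from preliminary data. The detectable intervention rates are 30.3% (adoption) and 12.6% (abstinence).

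Two statements frame these figures. The first is "We designed the RCT to detect medium-large effect sizes, which are consistent with estimates from our pilot study"; that sentence goes on to cite other brief-intervention studies with an intervention rate of at least 40% and a control rate of about 25%. The second says of the 30.3% "which compares favorably with 31.3% obtained in our pilot study as well".

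Section 1.2 describes the pilot as a single-arm study of 100 residents: "At 6 months, 31% of residents adopted a voluntary smoke-free home compared to 12% at baseline". Section 4.1.1 limits this trial to current smokers "who smoke in their homes".

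**The concern.** Three things in the paragraph do not sit together.

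- The cited contrast is 15 points at its low end, while the design's own detectable difference is 30.3 − 12 = 18.3 points. That is at a lower control rate, where the variance is smaller. No power is given for the cited contrast.
- The favourable comparison with the pilot rests on a margin of 31.3 − 30.3 = 1.0 point, obtained with normal quantiles although only 20 sites are randomised.
- A single-arm pilot has no 6-month control rate. The only 12% reported for it is the baseline share with a smoke-free home, and such residents would ordinarily not be eligible here.

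Readers will use the power statement to interpret a null primary result. If usual-care adoption were near 25%, a true 15-point benefit would be missed about half the time.

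**Working it through.** **Inputs (section 9.1.1; allocation from section 3.2).** 200 residents per arm in 10 sites; 80% retention, so 160 analysed per arm; 16 per site; ICC 0.077; two-sided alpha 0.05.

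**Effective sample size.** Design effect = 1 + 15 × 0.077 = 2.155 (the plan rounds to 2.16). Effective n = 160 / 2.155 = 74.2 per arm.

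**Formula.** SE = √{[p₁(1−p₁) + p₂(1−p₂)] / 74.2}; δ = (p₂ − p₁)/SE. Normal power = Φ(δ − 1.96). The small-cluster version uses a noncentral t with 20 − 2 = 18 df and critical value 2.101.

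**Step 1: the plan's figure.** For 12% v 30.3%: SE = √[(0.1056 + 0.2112)/74.2] = 0.0653; δ = 0.183/0.0653 = 2.80; power = 80.0%. The stated 30.3% reproduces. (A pooled variance gives 78.5% power and a detectable rate of 30.7%; arcsine gives 79.8% and 30.4%.)

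**Step 2: the cited contrast.** For 25% v 40%: SE = √[(0.1875 + 0.2400)/74.2] = 0.0759; δ = 0.150/0.0759 = 1.98; power = 51% (normal) or 46% (18 df). At 25% v 45% it is 74% (normal). Against 25%, 80% power is reached at 46.5% (normal) or 47.7% (18 df). If the ICC were different at these rates, normal power for 25% v 40% would be 72%, 59% and 45% at ICC 0.02, 0.05 and 0.10.

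**Step 3: ten sites per arm.** On 18 df, power for 12% v 30.3% is 75%, the detectable rate is 31.5%, and power at the pilot's 31.3% is 79%.

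**Step 4: sensitivity to the control rate** (80% power, ICC 0.077):

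| Control rate | Detectable rate, normal | Detectable rate, 18 df |
|---|---|---|
| 5% | 19.8% | 20.9% |
| 12% | 30.3% | 31.5% |
| 15% | 34.3% | 35.5% |
| 20% | 40.6% | 41.8% |
| 25% | 46.5% | 47.7% |

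**Step 5: abstinence** (secondary outcome, normal approximation). At ICC 0 the detectable rate against 4% is 12.5% unpooled or 12.6% pooled, so the stated figure reproduces. The ICCs above zero are assumptions.

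| ICC | Effective n per arm | Power, 4% v 12.6% | Power, 4% v 16.9% (pilot) |
|---|---|---|---|
| 0 | 160 | 81% | 97% |
| 0.02 | 123.1 | 70% | 92% |
| 0.05 | 91.4 | 57% | 83% |

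**The case against.** The strongest reply is that nothing is miscalculated. A reader might infer an arithmetic error from this point, but step 1 shows that 30.3% is correct on its inputs with a normal approximation.

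A reader might also infer that the protocol promises 80% power for 25% v 40%. It does not: the only contrast powered for the primary outcome is 12% v 30.3%, and the other studies appear in a parenthesis with an open-ended intervention rate and an approximate control rate. The 51% is therefore the low end of a range. What stands is that the sentence presents those effects as ones the design was built to detect, and 80% power is reached only at about 46.5%.

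The most tempting inference is that the trial is underpowered because the 12% comes from residents it excludes. The documents do not support this. That source is inferred from the matching figure and the pilot's single-arm design. Someone could also have a no-smoking rule and still smoke at home. Excluding residents with smoke-free homes could push the control rate below 12%, and section 5.1 says usual care has no smoke-free-home intervention. At 5% the detectable rate falls to about 20% to 21%. Nor can new adoption among pilot residents who smoked at home be worked out from the documents: the persistence of the baseline smoke-free homes is not given, and the 12% and 31.3% may have different denominators, since section 5.6 reports 84% pilot retention at 6 months.

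The 18-df shift is small: 31.5% is only 0.2 points above the pilot's 31.3%, an imprecise estimate from a study of 100 residents. It removes the claimed margin; it does not make the design fail. For abstinence, the comparison with the pilot's 16.9% survives: power stays at 83% or more (79% on 18 df) up to ICC 0.05.

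**Conclusion.** The concern holds as one of overstatement and missing sensitivity analysis; it should be fixed. Power is about 51% (46% on 18 df) at exactly 25% v 40%. With 10 sites per arm, power at 30.3% is about 75% and the detectable rate 31.5%, so the margin over the pilot is not there. The 12% is a doubtful 6-month control rate for residents who must smoke at home to enrol, in a direction the documents do not settle, and the pilot's 31.3% may include residents who were already smoke-free at baseline.

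These figures assume that ICC 0.077 applies at all the rates shown, that sites are of equal size, and that retention is 80%. Like the plan's own calculation, they leave out the repeated-measures model in section 9.3.2. The 18-df reference is the reviewer's choice for 20 sites; the plan names none.

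**What to change.** Rewrite section 9.1.1 as follows.

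- Restate power and the detectable rate for the primary outcome on 18 df.
- State where the 12% comes from, and recompute the pilot rates, at baseline and 6 months, among residents who smoked at home at baseline.
- Tabulate the detectable rate for control rates of 5% to 25%, as in step 4.
- State that power for 25% v 40% is about 50%, or remove that comparison.
- Remove the favourable comparison with the pilot for the primary outcome only.
- Add abstinence power for ICC 0 to 0.05 as a secondary sensitivity analysis.

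The cost is one paragraph, a small table and a re-analysis of existing pilot data. Enrolment does not change. The stated figures become slightly less favourable.

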3.2 Sample Size

We will recruit 400 PSH resident participants, with 200 each in the intervention and wait-list control arms (~20 participants per site). We expect to enroll 100 PSH staff, approximately 5 staff per site.

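### Section 9.1.1 says the design detects effects like those of earlier brief-intervention trials (at least 40% v about 25%), but power at 40% v 25% is only about 50%, and the 12% control rate appears to be the single-arm pilot's baseline value

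*Combined protocol and SAP*

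**What the plan says.** Section 9.1.1 describes the target as medium to large effects, consistent both with the pilot and with estimates "from other studies of brief interventions to increase adoption of smoke-free homes", for which it gives at least 40% in the intervention group and about 25% in control.

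The calculation then assumes "expected 6-month control group outcome rates of 12% and 4% for smoke-free home adoption and point prevalence abstinence, respectively", and the sentence reads as attributing these to preliminary data. Its result is a minimum detectable intervention rate of 30.3% against 12%, which it compares with the pilot's 31.3%. It does not compare the result with 40% v 25%, and it gives no power for any control rate other than 12%.

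Section 1.2 describes the pilot: "we conducted a single-arm trial of an intervention to increase voluntary adoption of smoke-free homes". Its result was: "At 6 months, 31% of residents adopted a voluntary smoke-free home compared to 12% at baseline".

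**The concern.** Two things in section 9.1.1 do not fit together.

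First, the cited trials show a difference of 15 points at its smallest (40% v 25%, odds ratio 2.0). The design's own minimum detectable difference is 18.3 points (30.3% v 12%, odds ratio 3.2), and it is calculated at a lower control rate, where the binomial variance is smaller. An effect at the bottom of the cited range is therefore below what the design detects with 80% power, although the text says the design target is consistent with those trials.

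Second, a single-arm pilot has no control group from which to take a 6-month control rate. The only 12% that the documents report for it is the baseline value. Using that value as the 6-month control rate assumes a level of untreated adoption that the plan neither states nor varies.

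What is at stake is how the stated power is read. If untreated residents adopt smoke-free homes more often than 12%, the trial is weaker than section 9.1.1 suggests, and a reader of a null result would have no figures from which to judge that.

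**Working it through.** **Inputs, all from section 9.1.1 unless noted**

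- "two-tailed alpha of 0.05"; "Power analyses assumed 80% power".
- "N=400 smoking residents recruited from 20 PSH units"; section 3.2 gives 200 per arm.
- Retention of 80% at 6 months: 0.80 × 200 = 160 per arm, 16 per site.
- Intra-site correlation 0.077 for smoke-free home adoption.

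**Effective sample size**

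Design effect = 1 + (16 − 1) × 0.077 = 2.155 (stated as 2.16). Effective n per arm = 160 / 2.155 = 74.2.

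**Reproducing the plan's figure**

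Power = Φ(|p1 − p2| / SE − 1.96), with SE = √{[p1(1 − p1) + p2(1 − p2)] / 74.2} (unpooled variance).

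For 30.3% v 12%: SE = √[(0.1056 + 0.2112) / 74.2] = 0.0653; 0.183 / 0.0653 = 2.80; Φ(2.80 − 1.96) = 80.0%. The stated minimum detectable rate is reproduced.

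**The pilot effect**

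For 31.3% v 12%: SE = 0.0657; 0.193 / 0.0657 = 2.94; power 84%. This half of the consistency claim is supported at a 12% control rate. If the intervention rate stays at 31.3% but control is 15%, power is 67%; if control is 20%, it is 36%.

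**The earlier trials**

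For 40% v 25%: SE = √[(0.1875 + 0.2400) / 74.2] = 0.0759; 0.15 / 0.0759 = 1.98; Φ(1.98 − 1.96) = 50.7%. A pooled variance gives 49.7% and the arcsine method 50.1%. A t reference with 18 degrees of freedom (20 sites) would lower it to about 46%. Ignoring clustering (n = 160 per arm), it would be about 83%.

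The documents cite at least 40%, so higher intervention rates matter too:

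| Intervention rate v 25% control | Power |
|---|---|
| 40% | 51% |
| 42% | 61% |
| 45% | 74% |
| 46.5% | 80% |
| 47% | 82% |

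**Minimum detectable rate by control rate** (80% power, unpooled, correlation 0.077)

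| Control rate | Minimum detectable intervention rate | Difference (points) |
|---|---|---|
| 5% | 19.8% | 14.8 |
| 8% | 24.5% | 16.5 |
| 12% | 30.3% | 18.3 |
| 15% | 34.3% | 19.3 |
| 20% | 40.6% | 20.6 |
| 25% | 46.5% | 21.5 |

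**The case against.** The case for the plan is substantial, and much of it stands.

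- **The arithmetic is right.** A reader might infer a calculation error. There is none: 30.3% v 12% follows from the stated inputs.
- **40% is a floor.** The cited range is at least 40%, so about 50% is the power at its lower end and not for the whole range. This stands. But a design described as consistent with that range should say what happens at 40%.
- **The sentence also names the pilot.** It does, and at 12% control the design covers the pilot effect. Only the other half of the claim fails.
- **About 25% may not transfer.** A reader might infer that 25% is the right control rate and the trial is therefore underpowered. The documents do not support that. The reference titles show that the cited trials enrolled 2-1-1 callers, and the documents do not give those trials' outcome definition or eligibility. Here the outcome requires at least 90 days of adoption (section 2.1), and participants must smoke in their homes (section 4.1.1). Usual care includes no smoke-free home intervention or cessation referral (section 5.1). The control rate could lie below 12% as well as above it.
- **The plan says expected, not observed.** A reader might infer that a baseline value was passed off as an observed control result. The wording does not claim that, and pre-intervention prevalence is a common planning assumption. That 12% came from the pilot baseline is itself an inference, from the matching value, the apparent attribution to preliminary data and the single-arm design.
- **The planned model uses repeated assessments.** It might change power, but the calculation in section 9.1.1 is a 6-month group comparison and claims no such gain.

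**Conclusion.** Wrong as written, and should be fixed. The consistency claim holds for the pilot effect (about 84% power at 31.3% v 12%) and fails at the lower end of the cited trials' range: about 50% power at 40% v 25%, about 74% at 45%, with 80% reached near 46.5%. The 12% control rate is a planning assumption, apparently the pilot's baseline prevalence, and no control group supports it.

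These figures rest on the plan's own sample size, retention and cluster size, on the normal approximation that reproduces its 30.3%, and on the correlation staying at 0.077 when prevalence is higher or lower. The documents do not say whether it would.

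The point concerns what section 9.1.1 claims. It does not show that the sample size is inadequate, because the documents do not settle which control rate to expect.

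**What to change.** In section 9.1.1:

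1. Limit the consistency claim to the pilot effect, or keep the reference to the earlier trials and state that power is about 50% for 40% v 25% and about 74% for 45% v 25%.
2. Describe 12% as an assumed 6-month control rate and state its source. If that source is the pilot's baseline prevalence, say so.
3. Replace the single minimum detectable rate with the six-row table above, covering control rates from 5% to 25%, and note that the correlation is held at 0.077.

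The cost is a few sentences and one small table. The stated sensitivity becomes less favourable at control rates above 12%. Sample size, endpoint and analysis are unchanged.

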Study procedures for PSH staff participants. Eligible PSH staff participants include service staff (e.g., case managers), who are ≥ 18 years of age, are willing to engage in a 2-hour training, and are able to provide informed consent. Staff in each site will be contacted via email, and invited to participate in a 2-hour training. Study staff will screen PSH staff for eligibility, obtain written informed consent using the teach-to-goal method,⁷⁸ and offer dates for the training.

Randomization and allocation. We will randomize 20 PSH sites into intervention and waitlist control arms. We will use the method of restricted randomization—commonly applied in cluster-randomized trials with small numbers of clusters—to ensure an acceptable level of balance across groups at baseline.⁷⁶ First, we will create two sets of 10 housing sites balanced on preexisting variables describing relevant characteristics of sites and their residents, e.g., property size, current smoking-related policies, and geographic location. Second, we will randomly assign one set of sites to intervention and the other to the wait-list control.

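### The 30.3% detectable rate for the primary outcome makes no allowance for 18 between-site degrees of freedom; with it the figure is about 31.5%, power at 30.3% is about 75%, and the margin over the pilot essentially disappears.

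*Combined protocol and SAP*

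**What the plan says.** Section 9.1.1 sets out the power calculation. It reports that "Power analyses assumed 80% power" and works with a "two-tailed alpha of 0.05". The sample is given as "N=400 smoking residents recruited from 20 PSH units". Four in five of these are expected to remain at 6 months, which leaves an "average 6-month site cluster size of 16 residents". For the primary outcome it takes a control rate of 12% and an intra-site correlation of 0.077, which gives a design effect of 2.16. It concludes that "the minimum detectable effect for the intervention group is 30.3% compared to 12% for the control group". The detectable rate is then set against the pilot result, with the remark "which compares favorably with 31.3% obtained in our pilot study as well".

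Section 3.1 describes the allocation: "First, we will create two sets of 10 housing sites balanced on preexisting variables", with one set then assigned at random to intervention. Section 3.2 gives the resident numbers, "with 200 each in the intervention and wait-list control arms".

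The power model in 9.1.1 is a mixed logistic model with site random intercepts; the primary analysis in 9.3.2 adds random intercepts for residents. Neither section names degrees of freedom, a reference distribution or a small-sample correction.

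**The concern.** The design effect enlarges the variance of the arm contrast to reflect clustering. It does not reflect that this variance has to be estimated from few units. Sites are what is randomised, 10 against 10, so the contrast has 10 + 10 − 2 = 18 between-site degrees of freedom. A test that holds two-sided 0.05 then needs a critical value of 2.101 rather than 1.960, and power falls accordingly.

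Two statements are at stake. One is that the design has 80% power at 30.3% with alpha 0.05. The other is that the pilot result lies comfortably above the smallest detectable rate. Readers will use both to interpret a null primary result.

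**Working it through.** **Inputs (9.1.1, 3.1, 3.2).** Two-sided alpha 0.05; power 80%; 200 residents enrolled per arm; 80% retention, so 160 per arm at 6 months; 16 per site; 10 sites per arm; control rate 0.12; intra-site correlation 0.077.

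**Step 1: reproduce the plan's figure.**
- Design effect = 1 + (16 − 1) × 0.077 = 2.155 (printed as 2.16).
- Effective residents per arm = 160 / 2.155 = 74.25.
- At 30.3%, unpooled standard error = √[(0.12 × 0.88 + 0.303 × 0.697) / 74.25] = √[(0.1056 + 0.2112) / 74.25] = 0.0653.
- Standardised difference = (0.303 − 0.12) / 0.0653 = 2.80, which equals 1.960 + 0.842.
- Solving for the rate gives 30.30%, and power at 30.3% is 80.0%.

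The plan does not state its quantiles; the exact match is the evidence that they were normal. Other normal-based versions give 30.7% (pooled variance), 30.4% (arcsine), 31.6% (log-odds Wald) and 32.3% (continuity-corrected).

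**Step 2: same variance and design effect, t reference with 18 df.**
- Critical value 2.101; power = P(T > 2.101), where T is noncentral t with 18 df and noncentrality (p − 0.12) / SE(p).
- Solving for 80% power gives p = 31.49%. Check: SE = √[(0.1056 + 0.2157) / 74.25] = 0.0658; (0.3149 − 0.12) / 0.0658 = 2.96, which equals 2.101 + 0.862, the sum of the two t quantiles.
- Power at 30.3% (noncentrality 2.80) = 75.5%.
- Power at the pilot's 31.3% (noncentrality 2.94) = 79.3%.

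A simulated site-level t-test (beta-binomial data, 16 per site, correlation 0.077, 20,000 runs) agrees: 75.3% power at 30.3%, 80.4% at 31.5%, type I error 4.8%. With pooled variance and 18 df the detectable rate is 32.0% to 32.2%. Every t-based version tried gave 31.5% or more on the plan's inputs.

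**Step 3: what a 1.96 cut-off would do.** If the statistic follows t with 18 df, the two-sided error at 1.96 is 6.6%. So 80% power at 30.3% and alpha 0.05 do not hold together.

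**Step 4: sensitivity (18 df, noncentral t).**

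| Change | Design effect | Minimum detectable rate | Power at 31.3% |
|---|---|---|---|
| None | 2.155 | 31.5% | 79.3% |
| 84% retention, 16.8 per site (pilot figure, section 5.6) | 2.217 | 31.3% | 80.1% |
| Correlation 0.074 (assumed) | 2.110 | 31.3% | 80.1% |

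**Step 5: unequal sites.** The plan gives 16 only as an average and no measure of spread, so the coefficient of variation (CV) is an assumption. Design effect = 1 + [(CV² + 1) × 16 − 1] × 0.077.

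| Assumed CV | Design effect | Minimum detectable rate | Power at 30.3% |
|---|---|---|---|
| 0.1 | 2.17 | 31.6% | 75% |
| 0.2 | 2.20 | 31.7% | 75% |
| 0.3 | 2.27 | 32.0% | 73% |
| 0.5 | 2.46 | 33.0% | 70% |

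**The case against.** **The plan's arithmetic is right.** This stands. 30.3% follows exactly from the stated inputs by a common design-effect method. The fault lies in the reference distribution, not in a sum.

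**The root is the unspecified test in 9.3.2.** If the mixed logistic model were judged by a Wald z statistic, nominal power would match the plan. That is true, but the type I error would then be about 6.6% if the statistic behaves as t with 18 df. The two points are linked, yet naming a small-sample method in 9.3.2 would leave the 80% in 9.1.1 uncorrected.

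**The pilot comparison has not reversed.** A reader might infer from 31.5% against 31.3% that the pilot effect is no longer detectable, or that the trial is underpowered for it. The documents do not support that. The gap is 0.2 points, and it closes at the pilot's own 84% retention or with a correlation of 0.074. The correlation comes from preliminary data, and the pilot had only 100 residents, so it is unlikely to be known to within 0.003. Balanced allocation of sites might also recover some precision: if adjustment removed 5% of the between-site variance (an assumption, ignoring degrees of freedom spent), the figure would be 31.2%.

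**Unequal sites need not be costly.** A reader might take 32% to 33% as the true figure. That needs a CV of 0.3 to 0.5, which the documents do not give. Recruitment aims at about 20 residents in every site, so a small CV is also plausible and adds only 0.1 to 0.2 points.

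**Conclusion.** The stated combination of 30.3% v 12%, 80% power and two-sided alpha 0.05 does not hold for 10 + 10 randomised sites. On the plan's own inputs, with equal site sizes and 18 df, the minimum detectable rate is about 31.5%, a rise of 1.2 points. Power at 30.3% is about 75%, a loss of about 4.5 points; this is the firmer result.

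The favourable margin over the pilot (31.3 − 30.3 = 1.0 point) is essentially lost. It is not replaced by a material deficit, since power at 31.3% is about 79%.

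The conclusion rests on three things: the inference that normal quantiles were used, the unpooled variance that reproduces the plan's figure, and an analysis that spends no further between-site degrees of freedom. It concerns the primary outcome only.

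**What to change.** In section 9.1.1:
- Restate the primary minimum detectable rate as 31.5% v 12% (18 df, equal site sizes), or keep 30.3% and give its power as about 75%.
- For the primary outcome, replace the favourable comparison with the pilot by wording such as *is about equal to the 31.3% obtained in the pilot*.
- Add a sentence that unequal site sizes would raise the figure. If a range is given, label the CV as assumed and include small values: 31.6% to 33.0% for CV 0.1 to 0.5.

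The reference distribution named for the primary test in 9.3.2 should agree with the restated power. The sample size need not change. The cost is two or three sentences and a slightly less favourable planning figure; recruitment and conduct are unaffected.
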